Title: Heel Wedges and Carbon Fiber Custom Dynamic Orthoses to Control Knee Biomechanics

NCT Number: NCT05209360

Date: October 19, 2023

Study Protocol

Purpose and Procedures:

The primary purpose of this line of research is to investigate the effects of combined carbon fiber custom dynamic orthosis (CDO) and medial-lateral wedge use on biomechanics during gait in an effort to reduce unilateral knee compartment loading. In this research study, pilot data will be collected from a cohort of healthy adult participants with no history of lower limb injuries or functional deficits. Participants will be evaluated using a series of study measures under each of the four conditions; without a brace (NoCDO), with a brace and no wedge (CDO), with a brace and a medial wedge placed in the shoe (Medial), and with a brace and a lateral wedge placed in the shoe (Lateral). Testing order will be randomized for each participant. Participants will walk on a level-ground walkway at self-selected and controlled speeds. Physical performance measures will incorporate tests of agility, speed, and lower limb power to ensure that the device and wedge don't negatively affect physical function. Questionnaires will be used to evaluate participants' pain and perception of comfort and smoothness for each condition.

Objectives and Specific Aims:

Specific Aim 1: Determine the effect of CDO alignment on lower limb mechanics during gait in a cohort of healthy individuals.

Specific Aim 2: Determine the effect of CDO alignment on physical function and patient reported outcomes in a cohort of healthy individuals.

Background and Significance:

Osteoarthritis (OA) affects nearly 27 million people in the United States alone, and accounts for approximately \$2,600 - \$7,500 in out of pocket expenses each year.[2] Knee OA can affect the medial, the lateral, or both compartments of knee. Treatment of OA can include a number of options such as medial-lateral wedging under the foot, knee orthoses, or ankle foot orthoses (AFOs). In the case of unilateral medial compartment knee OA unloader knee braces are commonly used to decrease knee adduction moments in an attempt to offload the knee. Similar efforts have been completed with the use of medial-lateral wedge placed in the shoe under the heel of the foot. Wedging was shown to stabilize biomechanics over time, preventing increases in knee adduction moment over a one-year period compared to neutral wedging. In another study, an ankle foot orthosis with a lateral strut was used in an effort to move the center of pressure position, thereby altering frontal plane knee moment. Use of this AFO resulted in improved pain, stiffness, and physical function scores when assed using the Western Ontario and McMasters Universities Arthritis Index (WOMAC).

CDOs consist of a cuff that falls just below the knee, a carbon fiber spring that runs the length of the calf and bends to store and return energy during gait, and a footplate the acts as a lever arm to bend the posterior strut. CDOs stabilize the ankle, and this may allow for greater affects at the knee when frontal plane alignment is adjusted. Similar to application of medial-lateral heel wedges in the shoe, placing medial-lateral wedges under a CDO may also reduce knee adduction moments. The purpose of this study is to determine if medial-lateral wedging combined with CDO use alters knee biomechanics, physical function, and patient reported outcomes.

Inclusion Exclusion Criteria:

Patient Inclusion Criteria

- 1) Between the ages of 18 and 45
- 2) Healthy without current complaint of lower extremity pain, spine pain, open wounds or active infections, or medical or neuromusculoskeletal disorders that have limited their participation in work or exercise in the last 6 months
- 3) Able to hop without pain

- 4) Able to perform a full squat without pain
- 5) Ability to speak and understand English

Patient Exclusion Criteria

- 1) Medical or neuromusculoskeletal disorders that have limited their participation in work or exercise in the last 6 months
- 2) Diagnosed with a moderate or severe brain injury
- 3) Lower extremity injury resulting in surgery or limiting function for greater than 6 weeks
- 4) Injuries that would limit performance in this study
- 5) Diagnosed with a physical or psychological condition that would preclude functional testing (e.g. cardiac condition, clotting disorder, pulmonary condition)
- 6) Uncorrected visual or hearing impairment(s)
- 7) Require use of an assistive device
- 8) Unhealed wounds (cuts/abrasions) that would prevent CDO use
- 9) BMI > 35
- 10) Pregnancy

Design and Methods:

Personal/demographic and anthropometric information will be used to fully characterize the study participants. We will collect multiple variables that have been previously associated with outcomes, including race, ethnicity, and education to characterize the cohort. Anthropometric and demographic information, such as age, biological sex, height, weight, leg length, shoe type, shoe length and width will also be used to characterize the cohort.

Patient-reported outcomes questionnaires will be used to evaluate participant pain and comfort and smoothness. Comfort and smoothness will be assessed using a modified version of the Socket Comfort Score, a reliable, valid, and sensitive measure of device fit and comfort.[3] These measures have been shown to effectively capture patient perception, are responsive to simple modifications to CDO device function, and will be applied in a manner consistent with a prior publication by the research team.[1] Participant will be asked to report their pain using a standard 11-point numerical pain rating scale, in which 0 = no pain and 10 = worst pain imaginable, at the start of session and at multiple points during testing.[4, 5] Semi-structured interviews will also be used to fully capture the participants perspectives, experience, and opinions associated with the study testing conditions.

Physical performance measures provide an objective and responsive assessment of an individual's functional mobility. Activities of daily life require performance of a range of functional tasks that require balance, agility, speed, and power. The four square step test (4SST) is a standardized and widely used test of functional mobility that requires rapid changes in direction that are often problematic following lower limb injury. The measure has good to excellent reliability and validity across multiple patient populations and groups and is a key dependent measure in most CDO-related studies to date and has demonstrated ability to detect changes in function in individuals with limb trauma and CDOs.[6-8, 9] The sit to stand 5 times (STS5) test is a well-established measure of lower limb muscle strength, endurance, and mobility.[10] The STS5 test has excellent reliability and good validity across a broad range of patient populations.[10-20]

Ground reaction force and motion capture data will be used to evaluate the motion and loading of the lower limb as participants walk on an over ground walkway at self-selected speed and a controlled speed based on leg length.[21, 22] The ability to collect reliable data across sites has been previously

demonstrated.[23] Previously established methods will be used to assess lower limb motion and moments.[22]

Statistical Analysis Plan

Analysis Methods:

All the primary dependent variables will be evaluated using similar statistical approaches within each group. One-way repeated measure ANOVAs will be used to evaluate the effect of CDO alignment. Paired t-tests with Bonferroni-Holm correction will be used for post-hoc comparisons. Multiple trials will be collected for each condition during testing.

Power Analysis:

The number of participants proposed for this study are consistent with those from prior investigations by [name] related to CDO design. Thirteen participants was sufficient to detect differences associated with AFO stiffness in a recent study by [name] (PMID: 25193884).

Literature Cited:

1. Ikeda, A.J., J.R. Fergason, and J.M. Wilken, Effects of altering heel wedge properties on gait with the Intrepid Dynamic Exoskeletal Orthosis. *Prosthet Orthot Int*, 2018. 42(3): p. 265-274
2. Rivera, J.C., et al., Posttraumatic osteoarthritis caused by battlefield injuries: the primary source of disability in warriors. *J Am Acad Orthop Surg*, 2012. 20 Suppl 1: p. S64-9.

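### Does leaving the levels of the CDO alignment ANOVA unstated, so that the no-brace condition may be one of them, undermine the analysis?

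*Combined protocol and SAP*

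**What the plan says.** Under Purpose and Procedures, "Participants will be evaluated using a series of study measures under each of the four conditions; without a brace (NoCDO"), then brace with no wedge (CDO), brace with medial wedge (Medial) and brace with lateral wedge (Lateral). The same section gives the primary purpose as "the effects of combined carbon fiber custom dynamic orthosis (CDO) and medial-lateral wedge use on biomechanics during gait", and describes the performance measures as "tests of agility, speed, and lower limb power to ensure that the device and wedge" do no harm to function.

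Both aims name a narrower factor: "Specific Aim 1: Determine the effect of CDO alignment on lower limb mechanics during gait in a cohort of healthy individuals" and "Specific Aim 2: Determine the effect of CDO alignment on physical function and patient reported outcomes in a cohort of healthy individuals".

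Under Analysis Methods: "One-way repeated measure ANOVAs will be used to evaluate the effect of CDO alignment". Paired t-tests with a Bonferroni-Holm correction follow as the post-hoc comparisons. Neither sentence gives the number of levels, the pairs or the size of the Holm family, and no alpha is stated.

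Two sentences in Background and Significance bear on what alignment means: "CDOs stabilize the ankle, and this may allow for greater affects at the knee when frontal plane alignment is adjusted" and "The purpose of this study is to determine if medial-lateral wedging combined with CDO use alters knee biomechanics".

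**The concern.** The no-brace condition has no CDO alignment. If it is one of four levels, the F combines two questions: whether wearing the brace matters, and whether wedge direction matters. A significant result labelled as an alignment effect could then come from the brace alone. If instead the ANOVA covers only the three braced conditions, no stated test uses the no-brace data, although the primary purpose and the check on physical function both call for them.

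The text settles neither reading. The four-condition design points to four levels; the Background sentence about adjusting frontal plane alignment points to three. Two analysts could follow the plan on the same data and report opposite omnibus answers to Aims 1 and 2.

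**Working it through.** **Inputs.** From the documents: four conditions, three of them braced; one-way repeated-measures ANOVA; Holm-corrected paired t-tests. The only sample size figure is 13, which the Power Analysis takes from an earlier study of AFO stiffness. It comes with no effect size, SD, correlation, alpha or power, so it cannot be reproduced. Assumed here: alpha 0.05, n = 13 (range 10 to 20), sphericity, and a brace effect *b* measured in SDs of a paired difference.

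**Step 1: can the brace alone make a four-level F significant?** Put the no-brace mean at *b* and the three braced means at 0. The squared deviations from the grand mean sum to *b*²(1 − 1/4) = 0.75*b*². A paired difference with SD 1 implies a residual variance of 0.5. The noncentrality is therefore n × 0.75*b*² / 0.5 = 1.5n*b*², with 3 and 3(n − 1) degrees of freedom. At n = 13 the noncentrality is 1.5 × 13 × 0.25 = 4.875 for *b* = 0.5, 12.48 for *b* = 0.8 and 19.5 for *b* = 1.0.

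| Probability that the four-level F is significant, no wedge effect | *b* = 0.5 | *b* = 0.8 | *b* = 1.0 |
|---|---|---|---|
| n = 10 | 30% | 67% | 87% |
| n = 13 | 39% | 81% | 95% |
| n = 13, Greenhouse-Geisser (simulated) | 34% | 77% | 94% |
| n = 20 | 59% | 96% | over 99% |

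An F on the three braced conditions stays at about 5% whatever the brace effect (about 4% with Greenhouse-Geisser). If the response to the brace varies between people, so that differences from the no-brace condition have 1.4 or 2.2 times the SD, the corrected four-level figures at n = 13 fall to 22%, 49% and 69%, or to 12%, 24% and 34%. The first half of the concern is therefore right.

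**Step 2: does this lead to a false wedge finding?** Take the four-level F at 0.05, then Holm over all 4 × 3 / 2 = 6 pairs if it is significant. That gate is inferred from the term post-hoc; the plan does not state it. With no wedge effect and n = 13, simulation gives at least one significant pair among CDO, Medial and Lateral in 1.6% of studies at *b* = 0, 2.4% at 0.5, 3.2% at 0.8, 3.6% at 1.0 and 4.6% at 1.5. At *b* = 0.8, 77.7% of studies have a significant F and no significant wedge pair. In those studies the pairs show that wedge direction is not behind the F.

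**Step 3: would a rewrite be better?** The natural candidate tests alignment with a three-level F and puts all six pairs in one Holm family that does not depend on the F. If the plan meant three levels, its family has 3 pairs and a first Holm step of 0.05/3 = 0.0167. Six pairs make that step 0.05/6 = 0.0083. Simulated power for Medial against Lateral at n = 13, with a true difference of 0.8 SD and CDO midway:

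| Brace effect | Three-pair family (gated by the three-level F) | Six-pair family, ungated |
|---|---|---|
| 0 | 57% (54%) | 44% |
| 0.5 SD | 57% (54%) | 47% |
| 0.8 SD | 57% (54%) | 49% |

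The largest loss is 57 − 44 = 13 points, and it disappears only at a brace effect of about 1.5 SD. The rewrite also leaves two routes to an alignment claim, the three-level F and the wedge pairs, with neither gating the other. With no wedge effect, the chance that at least one is falsely significant is 4.7% with no brace effect, 5.4% at 1.0 SD, 5.8% at 1.5 SD and up to 6.0% at 3 SD.

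**The case for a change.** The best case for a change is that the plan assigns the alignment question to the ANOVA, and the pairs are as unspecified as the levels. A brace effect is plausible, since Background and Significance describes a device that stabilizes the ankle and stores and returns energy. Listing the levels and pairs needs no new data. If the plan is read as a gated six-pair procedure, an ungated version loses no significant pair, and the chance of any false pair when nothing differs stays below 5% (4.3–4.4% against 2.6–2.8% at n = 13). A three-level F also has somewhat more power for a pure wedge effect: 67.7% against 62.1% for a Medial–Lateral difference of 0.8 SD with CDO midway.

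Two things stand. The levels and pairs are not listed, and a four-level F must not be read alone as an alignment effect. The rest is weaker. An omnibus F never says which conditions differ, and the plan supplies tests that do. Alignment is nowhere defined, and the stated purpose concerns wedging combined with the brace, so a four-condition ANOVA followed by pairwise tests is a conventional analysis of it. The claim that no pair loses power fails against the three-pair reading, which the text equally allows.

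**Conclusion.** The plan can stand. Its silence on levels and pairs is missing detail, and ordinary practice fills it: report the Holm-adjusted pairs, rest wedge conclusions on the comparisons among CDO, Medial and Lateral, and treat comparisons with the no-brace condition as effects of the brace, alone or with a wedge. On the four-level reading the omnibus F can be significant in 39% to 95% of studies with no wedge effect (n = 13, brace effect 0.5 to 1.0 SD), but false wedge pairs stay at or below about 4.6%, and no section rests a conclusion on the F alone. On the three-level reading the F tests alignment directly; the no-brace comparisons would then be unplanned in the text but obvious from the stated purpose.

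A prescribed rewrite brings no clear gain. It exchanges a cleaner omnibus test for up to about 13 points of power on Medial against Lateral, relative to a three-pair family, and up to about 6% false alignment claims if both routes count.

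All these figures assume alpha 0.05, normal data and, apart from the 12% to 69% figures, the same brace response in everyone. The documents give no brace effect or SD, and the 13 is borrowed from an earlier study. The figures show how far the issue could reach and do not predict this pilot's results.

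### The omnibus repeated-measures ANOVA drops anyone who lacks one of the four conditions; a mixed model would keep their remaining data

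*Combined protocol and SAP*

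**What the plan says.** Under Purpose and Procedures the protocol states: "Participants will be evaluated using a series of study measures under each of the four conditions". The four are no brace, brace alone, brace with medial wedge and brace with lateral wedge. It adds: "Testing order will be randomized for each participant".

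The Analysis Methods section of the SAP names the omnibus test, "One-way repeated measure ANOVAs will be used to evaluate the effect of CDO alignment", and the follow-up, "Paired t-tests with Bonferroni-Holm correction will be used for post-hoc comparisons". It also says "Multiple trials will be collected for each condition during testing", without giving the number of trials or how they are combined.

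The Power Analysis section gives no sample size for this study. It says "The number of participants proposed for this study are consistent with those from prior investigations" and mentions an earlier study of AFO stiffness with thirteen participants.

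The documents contain no missing-data rule, no definition of the analysis set, no allowance for dropout and no statement of how an uncompleted condition is handled in the analysis. They do not mention deletion of incomplete participants; that follows from the standard form of the named test.

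**The concern.** A one-way repeated-measures ANOVA works on a full participant-by-condition table. If a participant has three usable conditions and one lost, the usual implementation removes the whole row, and three valid measurements go with it. In a small sample each such row is a visible share of the data.

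The paired t-tests behave differently, because each needs only the two conditions it compares. The omnibus result and the post-hoc results for one variable could therefore come from different sets of participants, and the plan does not say whether that is intended.

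Loss is possible for ordinary reasons, such as unusable force or marker data, or a session that ends early. Because condition order is randomized, an early end can remove any of the four conditions. Discomfort is another possible reason: Design and Methods has pain rated "at the start of session and at multiple points during testing". What is at stake is some omnibus power and a clear account of who is in which analysis.

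**Working it through.** **Inputs.** Conditions per participant: 4 (Purpose and Procedures). Sample size: not stated; N = 13 is assumed from the earlier study cited under Power Analysis. Whole-condition loss rate q: not stated; 0.5%, 1%, 2% and 5% are assumed, independent across conditions. Alpha: not stated; 0.05 is assumed. The plan gives no effect size, SD, correlation or power, so it has no figure of its own to reproduce.

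**Step 1: data discarded per incomplete participant.** The full table has 13 × 4 = 52 cells. If k participants each lack one condition, 52 − k cells are observed and the ANOVA discards 3k of them: 3/51 = 6% for one participant, 6/50 = 12% for two, 9/49 = 18% for three.

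**Step 2: how often this happens.** P(participant complete) = (1 − q)^4. Expected completers = 13(1 − q)^4. P(at least one incomplete) = 1 − (1 − q)^52. Expected pairs for any one paired t-test = 13(1 − q)^2.

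| q | Participants incomplete | Expected completers (ANOVA) | P(at least one incomplete) | Expected pairs (t-test) |
|---|---|---|---|---|
| 0.5% | 2.0% | 12.7 | 23% | 12.9 |
| 1% | 3.9% | 12.5 | 41% | 12.7 |
| 2% | 7.8% | 12.0 | 65% | 12.5 |
| 5% | 18.5% | 10.6 | 93% | 11.7 |

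The sample size matters too. With 1 − (1 − q)^(4N), the chance of at least one incomplete participant at q = 2% is 55% for N = 10 and 80% for N = 20.

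**Step 3: omnibus power.** Assume within-person residual SD 1, sphericity, and condition effects 0, 0, +0.675 and −0.675. With n completers the noncentrality is n(0.675² + 0.675²) = 0.911n, on 3 and 3(n − 1) degrees of freedom. Power is 79% at n = 13, 75% at 12 and 70% at 11.

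A simulation with 4,000 runs per setting and conditions missing completely at random compared the complete-case ANOVA with a participant-plus-condition least-squares fit to all available cells. The latter stands in for the mixed model.

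| q | Complete-case ANOVA | All available data |
|---|---|---|
| about 0 | 78% | 78% |
| 2% | 75% | 78% |
| 5% | 67% | 74% |

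Simulation error is about 0.7 percentage points per figure, since √(0.75 × 0.25/4000) = 0.007. As a check, averaging the noncentral-F power over the binomial number of completers gives 74% and 67% for the complete-case column. A 20,000-run repeat gives 77% and 75% for the other. The gain is therefore about 3 points at 2% loss and 7 to 8 points at 5%.

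**Step 4: what the alternative does not repair.** Suppose the lateral condition is missing exactly when its own residual falls in the worst fraction m. The mean residual among those retained is −φ(z)/(1 − m), with z the 1 − m normal quantile. The true lateral-minus-brace-alone difference of −0.675 is then expected to appear as −0.78, −0.87 and −1.02 for m = 5%, 10% and 20%. In simulation both methods land there: −0.78, −0.88 and −1.03 for the complete-case ANOVA, and −0.79, −0.87 and −1.03 with all available data.

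**The case against.** The strongest reply is that missing conditions may hardly occur. Participants are pain-free adults aged 18 to 45 who can hop and squat without pain, and the exclusions cover injuries that would limit performance and wounds that would prevent use of the brace. Several trials are collected per condition, so one bad force or marker trial need not lose the condition. The documents give no sign of expected losses, and repeated-measures ANOVA is a valid standard choice for a four-condition pilot. All of this stands. It makes the harm conditional, and the rates above are illustrations rather than forecasts. At q = 0.5% an incomplete participant is more likely not to occur than to occur. What remains is that the plan has no rule for the case when one does.

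Two stronger readings are tempting. A reader might infer that people who tolerate a wedge badly vanish from all results, so that even the brace-alone against no-brace comparison is distorted. The documents do not support this: that comparison is a paired t-test needing only those two conditions, and nothing restricts the t-tests to participants complete on all four. For the same reason the loss of power in the omnibus test should not be carried over to the post-hoc tests.

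A reader might also infer that a mixed model cures selection by discomfort. Step 4 shows that it does not when absence depends on the unobserved response itself.

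**Conclusion.** The point holds as a cheap improvement, not as an error in the plan. The named omnibus test loses three usable measurements for each participant who lacks one condition, and omnibus and post-hoc results may then describe different people. With complete data nothing is lost. Under the assumptions listed (N = 13, alpha 0.05, independent whole-condition loss, sphericity, an effect with about 78% power on full data), the avoidable loss of omnibus power is about 3 points at 2% loss and 7 to 8 points at 5%. None of these inputs comes from a figure the plan sets for this study, so the size is indicative only.

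**What to change.** Amend Analysis Methods before results are seen:

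- Average the usable trials within each condition, and analyse these per-condition means with a linear mixed model: condition as fixed effect, participant as random effect (or an unstructured within-person covariance), Kenward-Roger degrees of freedom, all available conditions included.
- Take the Holm-corrected pairwise contrasts from the same model, so that the omnibus and post-hoc results rest on the same participants.
- Report, by condition, the number of missed conditions and the reason for each.
- If any condition is missed for discomfort, add a simple sensitivity analysis, for example refitting with the missed value set to the model's prediction shifted unfavourably by a range of amounts.

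The cost is SAP wording and slightly more analysis work. With complete data and compound symmetry the random-participant model reproduces the planned ANOVA. An unstructured covariance has 4 × 5/2 = 10 parameters, which is demanding with about 13 participants, so the choice should be named in advance. The model relies on data being missing at random, which is weaker than what the complete-case ANOVA needs but is still an assumption. If the sponsor prefers to keep the ANOVA, the minimum is to state how an incomplete participant is handled and who enters the t-tests, and to report missed conditions with reasons.

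### If the Holm-adjusted paired t-tests wait on a four-condition ANOVA F, variable response to the brace can hide a consistent wedge effect; the SAP should test the contrasts directly.

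*Combined protocol and SAP*

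**What the plan says.** The SAP, under Analysis Methods, names one test for alignment: "One-way repeated measure ANOVAs will be used to evaluate the effect of CDO alignment". The next sentence adds "Paired t-tests with Bonferroni-Holm correction will be used for post-hoc comparisons". No sentence says that the t-tests are run only after a significant F, or what is concluded if F is not significant but a Holm-adjusted contrast is. The section does not list the ANOVA's levels, the pairs in the Holm family, the alpha or any sphericity correction.

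The protocol, under Purpose and Procedures, lists "four conditions; without a brace (NoCDO), with a brace and no wedge (CDO"), followed by the brace with a medial wedge and the brace with a lateral wedge. Background and Significance gives the question: to "determine if medial-lateral wedging combined with CDO use alters knee biomechanics, physical function, and patient reported outcomes". Power Analysis gives no planned number of its own, only a precedent: "Thirteen participants was sufficient to detect differences associated with AFO stiffness in a recent study".

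**The concern.** Three of the four conditions are braced, and the wedge question is answered by contrasts among those three. A Lateral-Medial paired t-test uses only Lateral and Medial data. A four-condition F uses one pooled error term, which also contains how differently people respond to wearing the brace at all. If that response varies widely, the F can miss a small wedge effect that nearly everyone shows.

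Holm does not need the F to control family-wise error within an outcome, so a gate costs power without supplying protection that is otherwise missing. At stake is a report of no alignment effect while the Holm-adjusted Lateral-Medial contrast is clearly significant. Even without a formal gate this could happen, because the ANOVA is the only test the SAP names as evaluating alignment.

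**Working it through.** **The plan's own figure.** The only number is 13, a precedent from another study. It cannot be reproduced, because no alpha, power, effect size, SD or correlation is given.

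**Inputs.** From the protocol: four conditions, three of them braced. Assumed:
- n = 13 and two-sided alpha 0.05;
- all four conditions in the ANOVA, and Holm over all six pairs;
- a Lateral-Medial difference of 1.0 SD of the paired differences (dz = 1.0), with CDO midway between them;
- no mean brace effect;
- equal outcome variance in each condition, with correlation ρB between braced conditions and ρN between NoCDO and each braced condition.

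**Step 1: the contrast without a gate.** Holm's first threshold is 0.05/6 = 0.0083, which on 12 df is |t| > 3.15. The noncentrality is 1.0 × √13 = 3.61, which gives 67% power at that threshold. Holm's later, easier steps raise this to about 68%. NoCDO variability hardly matters here.

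**Step 2: the error of the four-condition F.** The expected error mean square is half the average variance of the six pairwise differences. Set the braced-braced difference variance to 1. Each NoCDO-braced difference then has variance r = (1 − ρN)/(1 − ρB), so

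error = ½ × (3 × 1 + 3 × r)/6.

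The condition means are 0, 0, −0.5 and +0.5, so the between-condition term is 13 × (0.25 + 0.25) = 6.5, and the F's noncentrality is about 6.5/error. The critical F on 3 and 36 df is 2.87.

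**Step 3: power to declare that Lateral differs from Medial** (20,000 or more simulated trials per setting; GG = Greenhouse-Geisser).

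| ρB / ρN | r | Error | 6.5/error | Holm alone | F gate | GG gate |
|---|---|---|---|---|---|---|
| 0.8 / 0.8 | 1 | 0.50 | 13.0 | 68% | 67% | 65% |
| 0.9 / 0.8 | 2 | 0.75 | 8.7 | 68% | 58% | 51% |
| 0.9 / 0.7 | 3 | 1.00 | 6.5 | 68% | 47% | 35% |
| 0.95 / 0.7 | 6 | 1.75 | 3.7 | 68% | 26% | 14% |

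**Step 4: when the loss shrinks.**
- *Mean brace effect of 0.6 SD* (SD of the outcome in one condition): the loss is about 1 to 2 points at 0.9/0.7 and about 4 at 0.95/0.7, or about 4 and 9 with GG.
- *Larger wedge effect* (dz = 1.5, 0.9/0.7, no brace effect): 97% against 92%.
- *More participants* (n = 20, dz = 1.0, 0.9/0.7): 93% ungated, 78% with the F gate, 67% with GG. A larger cohort reduces the problem but does not remove it.
- *ANOVA on the three braced conditions only*: the F itself has 87% power at dz = 1.0, and the mechanism disappears.

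**Step 5: error control.** With no true differences, ungated Holm over six pairs has a family-wise error of 3.5-4.5% across the settings tried. With the F gate it is about 2-3%.

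**The case against.** The strongest objection is that the premises are inferred. A reader might take the SAP to prescribe a two-stage rule with NoCDO in the error term, and read the larger losses as what this trial will suffer. The documents support neither. The word post-hoc is compatible with running every pair regardless of F. The factor is called CDO alignment, and a no-brace condition has no CDO alignment, so a three-level ANOVA is possible. The large losses also need two things together: NoCDO differences clearly more variable than braced ones, and little or no mean brace effect. The protocol describes a device that stabilises the ankle and returns energy, so a mean effect is plausible for at least some gait variables. An omnibus test followed by post-hoc comparisons is conventional and valid, and the protocol calls these pilot data.

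A reader might also infer that dropping the gate leaves error control untouched. It does not: false positives per outcome rise, though they stay under 5%, and the SAP has several primary dependent variables with no stated correction across them.

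All of this stands, and it limits the size of the point. It does not remove it. Four levels with post-hoc tests conditional on F remains the natural reading, because the protocol evaluates participants under four conditions and names no subset for the ANOVA. The 0.9/0.8 case, where NoCDO differences have only √2 ≈ 1.4 times the SD of braced ones, already costs 10 points. The SAP applies similar methods to all primary dependent variables, and a large mean brace shift cannot be counted on in each.

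**Conclusion.** The point holds conditionally, as a cheap improvement and not as an error of validity. If the F gates the t-tests and includes NoCDO, power for the wedge contrast can fall well below what Holm alone gives: from 68% to anywhere between 67% and 26% under the assumed inputs, and to as little as 14% with a Greenhouse-Geisser F. With similar correlations across conditions the loss is near zero, and with a clear mean brace effect it is small. The documents give no variances, correlations, effect size, alpha or definite sample size, so the loss in this trial cannot be known. Ungated Holm rejects whenever gated Holm does, so the change cannot lower power, and family-wise error within each outcome stays below 5%.

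**What to change.** Amend Analysis Methods to say, in substance:

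*For each outcome, the listed pairwise contrasts, in particular those among CDO, Medial and Lateral, will be tested directly by paired t-test with Holm-adjusted p-values and reported with 95% confidence intervals, whatever the omnibus F shows. The F is descriptive and does not decide whether an alignment effect is declared.*

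Name the pairs in the Holm family and the conditions in the ANOVA. The sponsor should choose the family deliberately. Restricting it to the three braced pairs raises ungated Lateral-Medial power from about 68% to about 79% under the same assumptions (n = 13, dz = 1.0), but the protocol also wants to check that the device itself does not harm physical function, and that needs NoCDO comparisons for those outcomes.

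The cost is a sentence or two and no new data. The downside is that global-null family-wise error per outcome rises from about 2-3% to about 4%, so slightly more false positives should be expected across the several outcomes, which are not corrected for one another.
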